10. CONCOMITANT MEDICATIONS AND NON-DRUG THERAPIES

Subjects will be instructed to inform the investigator prior to starting any new medications from the time of first dose of study treatment until the end of the study (Final Study Visit). Any concomitant medication(s), including non-prescription medication(s) and herbal product(s), taken during the study will be recorded in the electronic case report form (eCRF). Additionally, a complete list of all prior anti-cancer therapies will be recorded in the eCRF.

If future changes are made to the list of permitted/prohibited medications, formal documentation will be provided by GSK and stored in the study file. Any such changes will be communicated to the investigative sites in the form of a letter.

10.1. Permitted Medication(s)

Subjects should receive full supportive care during the study, including transfusion of blood and blood products, and treatment with antibiotics, antiemetics, antidiarrheals, and analgesics (not including platelet inhibitors), as appropriate.

Some azoles are well known to interact with ATRA; please follow your local institutional guidelines for choosing the best anti-fungal agent while the subject is on ATRA to minimize drug-drug interactions.

10.2. Prohibited Medication(s)

Subjects should not receive other anti-cancer therapy (chemotherapy, immunotherapy, biologic therapy, and hormone therapy other than for replacement) while on treatment in this study.

Anticoagulants (e.g., warfarin, direct thrombin inhibitors, etc) or platelet inhibitor (e.g., aspirin, clopidogrel) are prohibited from 14 days prior to the first dose of study drug through completion of the Final Study Visit.

In the combination arm with ATRA, antifibrinolytic agents (such as tranexamic Acid, aminocaproic acid, or aprotinin), agents known to cause pseudotumor cerebri/intracranial hypertension (e.g., tetracycline) and vitamin A or multivitamin including vitamin A will be prohibited while receiving ATRA.

10.2.1. Drugs that may alter the Pharmacokinetics of GSK2879552

All co-meds should be used with caution since little is known about the mechanism of clearance of GSK2879552. In vitro data in human microsomes and hepatocytes suggest that GSK2879552 has a negligible turnover.

10.2.2. Drugs that may have their PK altered by GSK2879552

The potential for pharmacokinetic interactions with drugs likely to be co-administered with GSK2879552 in vivo has not been assessed. In vitro data suggests that GSK2879552 has very low potential to inhibit CYP enzymes. GSK2879552 has also been shown to not activate human PXR which is known to induce several drug metabolizing enzymes.

GSK2879552 is not an inhibitor of human efflux transporters P-glycoprotein (P-gp) and breast cancer resistance protein (BCRP), uptake transporters organic anion transporting polypeptide 1B1 (OATP1B1) and OATP1B3, organic cation transporters (OCT2) and multidrug and toxin extrusion transporters (MATE1 and MATE2-K) should be used with caution.

10.3. Non-Drug Therapies

Non-drug anti-cancer therapies (e.g., radiation therapy, surgery, and/or tumor embolization) will not be permitted from the screening visit through the post-study follow-up visit.

NOTE: Subjects may receive palliative radiation treatment during this study.

Subjects will abstain from using herbal preparations/medications within 14 days prior to the first dose of GSK2879552 throughout the study until the final study visit. Herbal products include, but are not limited to:

- St. John's Wort, kava, ephedra (ma huang), ginkgo biloba, dehydroepiandrosterone (DHEA), yohimbe, saw palmetto, and ginseng

The investigator should contact a GSK Medical Monitor before initiating treatment with any herbal preparation including marijuana.

11. LIFESTYLE AND/OR DIETARY RESTRICTIONS

11.1. Contraception

11.1.1. Female Subjects

A female of non-childbearing potential (i.e., physiologically incapable of becoming pregnant) is defined as any female who has had a hysterectomy, bilateral oophorectomy (ovariectomy) or bilateral tubal ligation, or is post-menopausal.

A practical definition accepts menopause after 1 year without menses with an appropriate clinical profile, e.g., age appropriate, >45 years in the absence of hormone replacement therapy (HRT). In questionable cases, the subject must have a follicular stimulating hormone (FSH) value >40 mIU/mL and an estradiol value < 40pg/mL (<140 pmol/L).

A female of childbearing potential is defined as any female who does not meet the criteria of non-childbearing potential as described in the previous paragraph.

Female subjects of childbearing potential must not become pregnant during the study and so must be sexually inactive by abstinence or use contraceptive methods with a failure rate of <1%.

Female subjects of childbearing potential receiving ATRA combination treatment must use two reliable forms of contraception simultaneously during treatment and 30 days after the last dose of ATRA or 7 days after the last dose of GSK2879552, whichever is later. **Contraceptive counselling should be repeated monthly** while receiving ATRA and documented in the site source file. **Hormonal contraceptives are NOT considered acceptable form of contraception for female subjects of childbearing potential receiving ATRA combination treatment.** Intrauterine device or intrauterine system, male partner sterilization and double-barrier method as described below are acceptable forms of contraception for female subjects of childbearing potential receiving ATRA combination treatment.

Abstinence

Sexual inactivity by abstinence must be consistent with the preferred and usual lifestyle of the subject. Periodic abstinence (e.g. calendar, ovulation, symptothermal, post-ovulation methods) and withdrawal are not acceptable methods of contraception.

Complete abstinence from sexual intercourse for 7 days prior to first dose of study treatment, through the dosing period, and for at least 7 days after the last dose of study treatment.

Contraceptive Methods with a Failure Rate of $\leq 1\%$

- Oral contraceptives (either combined or progesterone only) if not contraindicated for this subject population or per local practice. – GSK2879552 monotherapy ONLY
- Estrogenic vaginal ring if not contraindicated for this subject population or per local practice. – GSK2879552 monotherapy ONLY
- Percutaneous contraceptive patches if not contraindicated for this subject population or per local practice. – GSK2879552 monotherapy ONLY
- Implants of levonorgestrel if not contraindicated for this subject population or per local practice. – GSK2879552 monotherapy ONLY
- Injectable progesterone if not contraindicated for this subject population or per local practice. – GSK2879552 monotherapy ONLY
- Intrauterine device or intrauterine system that meets the $<1\%$ failure rate as stated in the product label
- Male partner sterilization (vasectomy with documentation of azoospermia) prior to the female subject's entry into the study, and this male is the sole partner for that subject. For this definition, “documented” refers to the outcome of the investigator's/designee's medical examination of the subject or review of the subject's medical history for study eligibility, as obtained via a verbal interview with the subject or from the subject's medical records.
- Double-barrier method: condom and occlusive cap (diaphragm or cervical/vault caps) plus vaginal spermicidal agent (foam/gel/film/cream/suppository)

These allowed methods of contraception are only effective when used consistently, correctly and in accordance with the product label. The investigator is responsible for ensuring subjects understand how to properly use these methods of contraception.

11.1.2. Male Subjects

To prevent pregnancy in a female partner or to prevent exposure of any partner to the study treatment from a male subject's semen, male subjects must use one of the following contraceptive methods:

- Abstinence, defined as sexual inactivity consistent with the preferred and usual lifestyle of the subject. Periodic abstinence (e.g. calendar, ovulation, symptothermal,

post-ovulation methods) and withdrawal are not acceptable methods of contraception.

Complete abstinence from sexual intercourse from the first dose, through the dosing period, and for 3 months after the last dose of study treatment.

- Condom (*during non-vaginal intercourse with any partner - male or female*) **OR**
- Double-barrier method: condom and occlusive cap (diaphragm or cervical/vault caps) plus spermicidal agent (foam/gel/film/cream/suppository) (*during sexual intercourse with a female*)

11.2. Caffeine, Alcohol and Tobacco Restrictions

Subjects will abstain from ingesting alcohol, tobacco products, caffeine- or xanthine-containing products (e.g., coffee, tea, cola drinks, chocolate) for 24 hours prior to the start of dosing until collection of the final PK and or PD sample during each serial PK sampling day (e.g., Part 1, Days 1 and 15).

Subjects should abstain from consumption of Seville oranges, grapefruit, grapefruit hybrids or grapefruit juice and/or pommelos, exotic citrus fruits which may inhibit efflux transporters, from 1 day prior to the first dose of study treatment until the last dose of study drug.

12. DATA MANAGEMENT

For this study, data will be collected using defined electronic case report forms (eCRFs), transmitted electronically to GSK and combined with data provided from other sources in a validated data system.

Management of clinical data will be performed in accordance with applicable GSK standards and data cleaning procedures to ensure the integrity of the data, e.g. removing errors and inconsistencies in the data. AEs and concomitant medications terms will be coded using Medical Dictionary for Regulatory Activities (MedDRA) and an internal validated medication dictionary, GSK Drug. Electronic CRFs (eCRFs), including queries and audit trails, will be retained by GSK, and copies will be sent to the investigator to maintain as the investigator copy.

When laboratory samples (i.e., hematology and clinical chemistry) are analyzed by a central laboratory the results will be stored in a database maintained by the central laboratory and transferred to GSK at agreed times.

In all cases, subject initials will not be collected or transmitted to GSK according to GSK policy.

13. DATA ANALYSIS AND STATISTICAL CONSIDERATIONS

13.1. Hypothesis(es)

13.2. Part 1: Dose-Escalation Phase

No formal statistical hypotheses are being tested. Analysis of the data obtained from this study will be focused on comparison between dose cohorts and only descriptive methods will be used in analysis of the data obtained from this study.

Bayesian Prior for Combination Therapy Cohorts

The underlying Bayesian model requires that a Bayesian prior for the DLT rates for the combination be pre-specified. The monotherapy DLT rates on observed data from 200200 study and a prior Phase I ATRA study [Lee, 1993] were incorporated in the DLT prior distribution calculation. Table 6 shows the prior DLT data at a given dose.

Table 6 Prior Monotherapy DLT Data

GSK2879552 Dose level (mg)	# of DLTs / # Subjects	ATRA Dose Level (mg)	# of DLTs / # Subjects
1 mg	0/1	45 mg/m ²	1/6
2 mg	0/2	60 mg/m ²	0/3
4 mg	0/4	80 mg/m ²	0/3
8 mg	0/1		

Additional detail on the model will be provided in the RAP.

13.3. Part 2: Expansion Cohort

The primary goal of Part 2 is to detect a clinically meaningful response rate (defined as the percentage of subjects that have achieved a CR, CRp, PR or a morphologic leukemia-free state) of 30% in AML relative to a 10% response rate suggesting no activity.

Symbolically, the null hypothesis is:

$$H_0: RR \leq 10\%$$

The alternative hypothesis is:

$$H_A: RR \geq 30\%$$

13.4. Sample Size Determination

13.4.1. Part 1: Dose-Escalation Phase

The total number of subjects to be enrolled into Part 1 will depend on the number of dose escalations required to establish the maximum tolerated dose of GSK2879552 alone or in

combination with ATRA; they are not driven by statistical considerations. To complete dose escalation, it is estimated that approximately 55 evaluable subjects will be enrolled .

Monotherapy doses to be studied in Part 1 will be guided by calculating the posterior probability that the DLT rate falls within an acceptable range for each subsequent dose after each dose cohort observation period. The N-CRM method will be used to calculate posterior probabilities utilizing a pre-specified prior distribution.

Combination doses to be studied in Part 1 will be guided by calculating the posterior probability that the DLT rate is as close to, but below the target toxicity rate of 33% at adjacent dose combinations. The Bayesian logistic regression method will be used to calculate posterior probabilities utilizing the pre-specified prior distribution of the toxicity rates on combinations.

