An internal dose-escalation committee will be comprised of the following GSK representatives: Medical Monitor, Safety Physician or Scientist, Clinical Scientist, Biostatistician, PK and PD Scientists, and Study Operation Lead. The dose-escalation committee will review available relevant data on demographics, all adverse events including non-DLT toxicities, laboratory assessments, 12-lead ECGs, and dose administration logs, as well as PK data. Quality control of critical safety data will be described in the Dose Escalation Plan, which includes ongoing study monitoring visits, Sponsor review of the clinical database, and confirmation by site investigators and/or delegate that the data is accurate and complete.

On the basis of a review of these data and in joint discussions with the participating investigators, a determination will be made as to whether dose escalation/de-escalation should continue as recommended by the N-CRM. The dose-escalation decision and

rationale for each cohort will be discussed with investigators during teleconference(s) and documented in writing, with copies maintained at each study site and in the study master file.

Description of the Continual Reassessment Method

After each cohort, a dosing recommendation for the next cohort will be made using the N-CRM. All available data, including safety, PK and PD data from current and prior cohorts will be reviewed at the dose escalation meeting. Although the N-CRM will be used to recommend the next dosing level, clinical judgment by the Medical Monitor and internal dose-escalation committee in consultation with the investigators can halt or reduce dose escalation or de-escalate as deemed appropriate at any time during the trial.

The N-CRM design is a type of Bayesian adaptive dose escalation scheme that assumes a two-parameter logistic model for the toxicity rate based on dose. It is a modified version of the original Continual Reassessment Method (CRM) [O'Quigley, 1990]. A CRM-based design uses a statistical model for dose and toxicity, and is expected to locate the MTD efficiently while minimizing the number of subjects exposed to pharmacologically inactive dose levels.

The method is fully adaptive and makes use of all the DLT information available at the time of each dose assignment. In contrast, the 3+3 method only uses information from one dosing cohort at a time.

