At the time of each dose escalation decision, the Fixed and Adaptive Clinical Trial Simulator (FACTS, Version 2.3 or higher, Tessella) will be used to obtain, for each potential dose, the posterior probabilities that the DLT rate for that dose lies in each of four toxicity intervals (underdosing, target dose range, excessive toxicity, and unacceptable toxicity). The four DLT toxicity intervals are defined as follows:

- [0%,16%) Underdosing
- [16%, 33%) Target dose range
- [33%, 60%) Excessive toxicity
- [60%, 100%) Unacceptable toxicity

The recommended dose will be the dose with the highest posterior probability of lying in the target dose range with the additional requirement that the sum of the posterior probabilities of the DLT rate lying in the excessive toxicity or unacceptable toxicity range is less than 25%. Selection of the next dose is also subject to the built-in safety constraints of maximum allowed dose increment. An updated estimate of the toxicity curve will be provided at the time of the dose escalation meeting.

Note that de-escalation as well as escalation is possible using this method.

[figure not shown]
Bayesian Prior

The N-CRM methodology requires that a Bayesian prior for the toxicity curve be pre-specified. The Bayesian prior used for this design was determined using the quantile method. For each possible dose, an estimate of the median probability of DLT was specified, along with a 95% credible interval. The 95% credible intervals are intentionally wide due to limited information about the toxicity profile of GSK2879552 in humans. [Table 1](#) shows the median prior probability of experiencing a DLT at a given dose along with a 95% credible interval around the median. This table does not imply that all doses will be studied:

Table 1 Specified Prior Probability of DLT

Dose level (mg)	2.5% Quantile for Probability of Toxicity	Median Probability of Toxicity	97.5% Quantile for Probability of Toxicity
0.25 mg	0.005	0.01	0.2
0.5 mg	0.01	0.02	0.25
1 mg	0.02	0.03	0.3
1.5 mg	0.02	0.04	0.35
2 mg	0.03	0.05	0.4
2.5 mg	0.04	0.06	0.5
3 mg	0.05	0.07	0.6
4 mg	0.05	0.08	0.7
5 mg	0.06	0.1	0.78
6 mg	0.07	0.13	0.85
8 mg	0.08	0.16	0.95
10 mg	0.1	0.2	0.99
12 mg	0.12	0.24	0.99
15 mg	0.13	0.28	0.99
20 mg	0.14	0.35	0.99
25 mg	0.15	0.42	0.99

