A graphical presentation of the prior is displayed in the [Figure 2](#). In the figure, the x-axis is natural log (dose/reference dose), where the reference dose is set to 5 mg. Doses are the projected doses. Actual doses used during the conduct of the trial may vary.

Figure 2 Prior Distribution For The Probability of DLT Given Dose**4.2.2. GSK2879552 and ATRA combination**

In Cohort 1, three subjects will receive GSK2879552 2 mg once daily dose with ATRA 45 mg/m²/day as two divided doses. After all three subjects complete the first 4 weeks of treatment, the safety data will be reviewed for DLT. Available PK and PD data will be also reviewed prior to a dose escalation decision and starting Cohort 2. Each cohort will enroll 3 or more subjects to obtain sufficient data. If any subject becomes unevaluable for reasons other than toxicity, a replacement subject will be enrolled. In addition, subjects who fail to take at least 75% of their scheduled doses of each drug in the first 4 weeks for reasons other than toxicity will be replaced. Starting with Cohort1, the dose escalation will use the N-CRM with prior DLT information of GSK2879552 and ATRA monotherapies and follow the same rule with regards to the number of subjects, maximum dose increment, and the completion of dose escalation as described in Section 4.2.1. The details of priors used in N-CRM model is described in Section 13.2.

Starting at dose level 1, the following GSK2879552 dose levels are planned for evaluation in combination with ATRA..

Dose level	GSK2879552	ATRA
1	2 mg/day	45 mg/m ² /day
2	4 mg/day	45 mg/m ² /day
3	8 mg/day	45 mg/m ² /day
4	12 mg/day	45 mg/m ² /day
5	20 mg/day	45 mg/m ² /day

A reduced dose of GSK2879552 or ATRA may be considered if the combination is not well tolerated at dose level 1. The initial dose level reductions allow for either drug to be reduced. Subsequent dose levels are based on the totality of data and upon discussion with the investigators.

Dose level	GSK2879552 ATRA fixed at 45mg/m ²
-1	1 mg/day
-2	0.5 mg/day

Dose level	GSK2879552
	ATRA <30mg/m ²
1a	2 mg/day
-1a	1 mg/day
-2a	0.5 mg/day

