4.2.6. Maximum Tolerated Dose and Recommended Phase 2 Dose

The MTD is defined as the dose with the highest posterior probability of subjects experiencing a DLT in the first 28 days on treatment in the target interval [16%,33%], and for which the probability that the DLT rate lies within the excessive toxicity or the unacceptable toxicity windows is less than 25%. The interval boundaries of 16% and 33% are chosen to be consistent with the traditional 3+3 design toxicity boundary which is 1/6 and 1/3.

The RP2D will be MTD or a lower dose that provides adequate PK exposure and biologic activity with superior tolerability. Up to 12 additional subjects will be enrolled at the dose to further define the safety and tolerability of the dose and schedule. The RP2D may be different for mono-therapy and for the combination therapy with ATRA.

Data considered for RP2D selection will include, but not be limited to: safety, available PK profile, and observed signs of clinical activity from Part 1.

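### Protocol 13.4.1 gives the combination a next-dose target just below 33% with no overdose limit, whereas 4.2.1 and 4.2.6 require P(DLT rate ≥33%) below 25%; the combination model is also named inconsistently

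*Protocol*

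**What the plan says.** **Protocol 4.2.2** (combination) states that "the dose escalation will use the N-CRM with prior DLT information of GSK2879552 and ATRA monotherapies". It carries over three items from 4.2.1: cohort size, maximum increment and completion of escalation. The dose-selection rule is not in that list.

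**Protocol 4.2.1** describes the N-CRM as a model that "assumes a two-parameter logistic model for the toxicity rate based on dose". It recommends the dose with the largest posterior probability of a DLT rate in 16-33%, on condition that "the sum of the posterior probabilities of the DLT rate lying in the excessive toxicity or unacceptable toxicity range is less than 25" per cent. The excessive-toxicity range starts at 33%, so the condition is P(DLT rate ≥33%) < 25%.

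**Protocol 4.2.6** defines the MTD, without restriction to monotherapy, as a dose for which the probability that the rate "lies within the excessive toxicity or the unacceptable toxicity windows is less than 25" per cent.

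**Protocol 13.4.1** keeps monotherapy on the N-CRM with an acceptable-range criterion. For the combination it gives a different target, a DLT rate close to "but below the target toxicity rate of 33% at adjacent dose combinations", and a different method: "The Bayesian logistic regression method will be used to calculate posterior probabilities". It gives no overdose limit and does not say which posterior summary is compared with 33%.

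**Protocol 13.7.1** and **SAP 2.3 and 3.1** assign a Bayesian copula regression to the combination, in contrast to the N-CRM for monotherapy. SAP 2.3 also repeats that the combination uses the N-CRM. Protocol 13.2 and 13.7.1 leave model detail to the RAP (the SAP), which defines no combination model or selection rule.

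**The concern.** A statistician preparing a combination escalation meeting could take either of two criteria from the protocol. An estimated DLT rate below 33% does not imply that the probability of exceeding 33% is below 25%. The same data can therefore give two recommended doses, and the one from 13.4.1 may be a dose that 4.2.1 and 4.2.6 would refuse. At stake is how firmly the combination backs off after DLTs. The differing model names mean that the documents also do not settle which posterior the chosen criterion is applied to.

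**Working it through.** The plan gives no operating characteristics for the combination (Appendix 1 simulates a single-agent dose curve), so there is no stated figure to reproduce. The check asks whether the two criteria can disagree.

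**Step 1: one dose, no dose-response curve.** With prior Beta(a, b) and x DLTs in n, the posterior is Beta(a+x, b+n−x).

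| Prior | Data | Posterior mean | P(≥33%) | Below 25%? |
|---|---|---|---|---|
| Uniform (1, 1) | 1/6 | 2/8 = 0.250 | 0.270 | no |
| Uniform | 2/9 | 3/11 = 0.273 | 0.307 | no |
| Jeffreys (0.5, 0.5) | 1/6 | 1.5/7 = 0.214 | 0.204 | yes |
| Jeffreys | 2/9 | 2.5/10 = 0.250 | 0.255 | no, by 0.005 |

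A mean clearly under 33% can fail the limit. Whether it does depends on the prior.

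**Step 2: dose-response illustration.**

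Inputs from the protocol:
- Model: logit p(d) = α + β·ln(d/5), with reference dose 5 mg (4.2.1).
- Appendix 1 prior: α −1.6278 (SD 1.3652), ln β −0.0116 (SD 0.4136), correlation 0.2429.
- Candidate doses 0.5, 1, 2, 4, 8, 12 and 20 mg (4.2.2).
- Increment cap: 200% of the current dose with no DLT, 150% after one (4.2.1).

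Assumptions, because the combination prior and the 13.4.1 summary are not given:
- 13.4.1 is read as the highest dose with posterior mean below 33%.
- Six priors. (a) is Appendix 1 alone. (b) adds the GSK2879552 counts in Table 6 (0/1, 0/2, 0/4 and 0/1 at 1, 2, 4 and 8 mg). (c) to (f) are (b) with an independent ATRA component, p = 1 − (1 − p_GSK)(1 − q), with q ~ Beta(1.5, 5.5), Beta(1.5, 11.5), Beta(2, 6) and Beta(2, 12). These use ATRA data of 1/6, or 1/12 pooled over the three ATRA doses in Table 6.
- Twenty first-pass histories: 0/3 at every lower planned level, then 0 to 3 DLTs in 3 at 2, 4, 8, 12 or 20 mg (5 × 4 = 20).

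Results by grid integration:

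| Prior | Histories that differ (of 20) | 13.4.1 escalates / stays / de-escalates less far | P(≥33%) at 12 mg after 2/3 at 12 mg |
|---|---|---|---|
| a | 9 | 1 / 3 / 5 | 0.438 |
| b | 3 | 0 / 2 / 1 | 0.291 |
| c | 10 | 1 / 5 / 4 | 0.368 |
| d | 8 | 1 / 5 / 2 | 0.316 |
| e | 11 | 1 / 6 / 4 | 0.403 |
| f | 8 | 1 / 5 / 2 | 0.333 |

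Using the posterior median instead of the mean gives 10, 4, 11, 8, 11 and 8.

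Three histories differ under all six priors:
- 2/3 at 12 mg: 13.4.1 stays at 12 mg (overdose probability 0.29-0.44); the 4.2.1 rule goes to 8 mg.
- 2/3 at 20 mg: 13.4.1 stays at 20 mg (0.36-0.44); the 4.2.1 rule goes to 12 or 8 mg.
- 3/3 at 20 mg: 13.4.1 goes to 12 mg (0.28-0.42); the 4.2.1 rule goes to 8 mg.

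None of these is an escalation, so the increment cap does not remove them. At the 2 mg starting level the rules differ in at most one of the four outcomes under any prior.

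**The case against.** **The limit already applies.** Section 4.2.2 places the combination on the N-CRM, and the 25% condition is part of that rule. Section 13.4.1 itself says that Part 1 enrolment "will depend on the number of dose escalations required to establish the maximum tolerated dose", alone or with ATRA, and the MTD in 4.2.6 carries the limit for every arm. Section 13.4.1 is a sample-size paragraph, and its monotherapy sentence omits the limit too. Much of this stands: the limit arguably reaches the combination. But the monotherapy sentence is compatible with 4.2.1, whereas the combination sentence states another criterion under another method name. It is not merely a shortened version of the same rule.

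**The compared rule is constructed.** Section 13.4.1 never says highest dose with posterior mean below 33%, and every prior is assumed. This stands. The counts illustrate possible disagreement and do not estimate its frequency.

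**Not every difference is due to the missing limit.** This also stands. Under prior (e), after 1/3 at 12 mg, 13.4.1 keeps 12 mg with overdose probability 0.199, inside the limit. The 4.2.1 rule prefers 8 mg only because its target-range probability is 0.579 against 0.575.

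**Other safeguards.** The committee "can halt or reduce dose escalation or de-escalate as deemed appropriate at any time during the trial". That limits the consequences but does not say which recommendation the model should bring to it.

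**The SAP is thin for a reason.** It was written for an abbreviated report after early termination. That is fair, and the missing prior and the unstated handling of the reduced-ATRA levels are missing detail rather than part of the conflict.

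**Conclusion.** The conflict in the text is real and should be fixed; confidence is medium. Taken literally, 13.4.1 can keep or select a combination dose that fails the 25% limit in 4.2.1 and 4.2.6, and the sections do not agree on the model's name. The size rests on the assumed reading of 13.4.1 and the assumed priors: 3 to 11 of 20 first-pass histories differ, three of them under all six priors. SAP 5.1 lists only one combination level, 2 mg with ATRA 45 mg/m²/day, so the realised effect was probably small.

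Two stronger conclusions are tempting and are not supported:
- A reader might infer that the combination had no overdose control, or that 13.4.1 pushes doses up. Sections 4.2.2 and 4.2.6 point to the limit applying, the committee can always hold or reduce, and in the illustration 13.4.1 escalates in at most one differing history per prior. It mainly stays or de-escalates less far.
- A reader might infer that the copula regression cannot be squared with the N-CRM. No document defines the copula, and joining a logistic GSK2879552 curve to an ATRA component, as in priors (c) to (f), is a construction of that general kind. While ATRA is fixed, Bayesian logistic regression and the N-CRM could be the same model. What can be said is that the names differ and nothing in the documents reconciles them.

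**What to change.** In Protocol 13.4.1, replace the combination sentence with the criterion of 4.2.1 and 4.2.6: the dose with the highest posterior probability of a 16-33% DLT rate, subject to P(DLT rate ≥33%) below 25% and to the increment cap. Use one name for the combination model in 4.2.2, 13.4.1 and 13.7.1. Matching wording in SAP 2.3 and 3.1 would be for consistency only and changes no analysis.

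The cost is protocol wording. The drawback is somewhat slower combination escalation in some histories, possibly one extra cohort, which under 4.2.2 means at least 3 subjects.
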